## 4 Ethical considerations

### 4.1 General information

This study will be conducted in accordance with Regional Ethics Committee (REC) and the Declaration of Helsinki. All participants must sign an informed consent form before enrolment. The protocol will be submitted to the Capital Regional Ethics Committee and to the Danish Data Protection Agency. Information regarding participants of the project will be protected in accordance with the applicable laws of Denmark including laws concerning the processing of personal data (“databeskyttelsesforordningen” and “databeskyttelsesloven”). Amendments and modifications to

Sample Size	
Group 1	10
Group 2	10
Total	20
Study Parameters	
Mean, group 1	1.14
Mean, group 2	3.8
Alpha	0.05
Beta	0.2
Power	0.8

the protocol will be sent to the Regional Ethics Committee and the Danish Data Protection Agency for approval and no changes to the protocol will be established before approval.

#### 4.3 Access to patient information

The medical doctors affiliated with this study, will seek access to the patients' medical chart ("Sundhedsplatformen"), to obtain information regarding previous diagnoses that could jeopardize the participation in the study. The patients' blood samples that are drawn as part of this study will be analyzed by the Department of Clinical Biochemistry at Rigshospitalet. Information regarding these blood samples will also be obtained through access to the patients' medical chart. Any health information regarding the patient will only be obtained following informed oral and written consent from the patient.

#### 4.4 Novelty and importance

We expect this study to provide novel insight into the physiological response to exercise in SLE patients that differ in their IFN gene signature. As well as give clinicians an idea of the differing needs of patients in this heterogenous group of patients. Allowing physicians to further tailor medical practice to the individual. Furthermore, this research will help elucidate the complex relationship between auto-immune diseases and exercise.

#### 4.5 Risks and disadvantages of interventions

Evidence shows that exercise for stable patients with SLE is safe, and it has proven to be clinically beneficial on patient reported outcome measures of fatigue, but not necessarily on their SLE activity. Therefore, we are not asking our control group to seize their current physical activities, but rather we are adding on exercise in the intervention group.

We believe that these 12 weeks of not increasing exercise hold little risk for the control groups, who after the study will be instructed in the exercise methods that the intervention group received.

#### 4.6 Risks and disadvantages of baseline and follow-up tests

During the study, blood samples of up to 400 ml will be drawn from the patient. Half of this over multiple days on the baseline assessments and half of this 12 weeks after at follow-up assessments.

The risks of dizziness, infections or anemia are minimal. Patients will be informed to contact one of the medical doctors affiliated with this study, if the patient suspects infection surrounding the penetrated skin (redness, swelling, fever, heat).

A VO2max test is considered safe but may cause patients to feel dizzy immediately following the test. An oral glucose tolerance test is considered safe. A lung function test is considered safe but may cause patients to feel dizzy for a limited time. An echocardiography following standard clinical procedures is considered safe and does not in itself pose any risks. Rb-PET/CT will be performed by specialized medical technologists at the Dept. of Clinical Physiology, Nuclear Medicine and PET at Rigshospitalet, who routinely do this. The scan itself, including the injection of tracer, is not associated with any discomfort, but an intravenous line must be placed which is associated with the same risks as normal blood sampling as described above. Adenosine infusion may cause some

temporary discomfort, notably palpitations, breathlessness, headache, dizziness, and fatigue; adenosine has a half-life in the blood stream of less than 30 seconds, and these symptoms will cease within minutes after the 6-minute adenosine infusion is discontinued. The stress scan is performed under the immediate supervision of a nuclear medicine physician.

Prior to the muscle biopsy, local anesthesia will be administered, which is associated with short-lasting discomfort. After a few minutes, the area is numbed, and a small skin incision is made. The Bergstrom cannula is inserted in M. vastus lateralis and the biopsy is taken. This part of the procedure might be associated with slight pain. The procedure takes a few minutes and after the biopsy is taken, the wound will be closed with Steri-Strips, which must be kept on for five days. There will be an additional patch, which can be removed after two days. Subjects might experience some degree of muscle pain after the biopsy. Paracetamol, 1000 mg, max. four times a day will be recommended as pain killers. The procedure can leave small bruises, but generally heals nicely. Temporary decreased sensation at the incision area or where the local anesthetic has been injected can be seen. Usually, nerve lesions and altered sensation at the incision area heals within months. In theory, infections can appear when piercing the skin. This occurs in 1 out of 25,000 times and can in some cases require treatment with antibiotics. In order to avoid infection all participants will be informed to abstain from swimming in seawater or swimming pools within the first five days. Furthermore, they will be informed to contact a project doctor in case of any signs of infection (heat, redness, swelling or fever). We believe that the potential outcome of this study to future SLE patients are significant, compared to any potential risk or disadvantages that patients must endure by participating.

#### 4.7 Radiation exposure

A DXA scan will provide an effective radiation dose in the range of 3-30  $\mu$ Sv - equivalent of 3 days of background radiation in Denmark and is considered safe (Category I in “Appendiks 2: Retningslinjer om anvendelse af ioniserende stråling i sundhedsvidenskabelige forsøg”; NVK 2011). The radiation exposure due to each rest-stress  $^{82}\text{Rb}$ -PET/CT scan is 4 mSv. The maximal total effective radiation exposure associated with participation in this study is thus less than 9 mSv and is thus risk category IIb according to the International Commission on Radiation Protection and the European Commission. Due to this radiation exposure, the lifetime risk of cancer is increased from 25% to 25.045%. As the current study is directly targeted at unveiling means of preventing and curing cardiovascular disease in patients with SLE, we consider this reasonable. If pregnancy is deemed possible, a pregnancy test will be performed prior to the scans.

#### 4.8 Safety and precautions

Patients will undergo a medical assessment to ensure eligibility and safety. At all patient interventions (including exercise) at CFAS, a medical doctor is present and reachable. During exercise at one of the local collaboration-centers a medical doctor will not be present but be reachable through telephone. The Department of Clinical Physiology, Nuclear Medicine & PET, Rigshospitalet has great experience in conducting PET scans and will perform the necessary precautions both prior to and after the scan.

##### 4.8.1 Safety evaluation

All adverse events (AEs) and serious adverse events (SAEs) observed by the investigators will be reported in the case report form (CRF) and to REC as requested, from the start of the trial (after written consent) to the final day of protocol procedure. An AE is defined as any untoward medical

occurrence in a participant, which does not necessarily have a causal relationship with the trial intervention. AEs are graded as the following:

Grade 1: The AE is noticeable to the subject but does not interfere with subject's every day's life activities; it may or may not require additional concomitant therapy.

Grade 2: The AE interferes with the subject's daily activities; it usually requires additional therapy.

Grade 3: The AE is intolerable and requires additional therapy.

Grade 4: The individual is at immediate risk of death at the time of the AE; it does not refer to an event which hypothetically might have caused death if it was more severe. Life-threatening events result in a SAE.

An SAE is any untoward medical occurrence or effect that at any dose results in death, is life-threatening, requires hospitalization or prolongation of existing hospitalization, results in persistent or significant disability or incapacity, or is a congenital anomaly or birth defect.

#### 4.9 Procedure for recording and handling AEs and SAEs

Full description of these procedures is attached in Appendix A. All AEs/SAEs related to the study assessments (including the exercise intervention) will be recorded immediately and notified in the CRF. All AEs/SAEs (both those that are anticipated and unanticipated) will be recorded on adverse event forms and published with study results. We will also collect patients' self-report of AEs/SAEs, and report these in the CRF. These forms will include a description and classification of the event, date of onset, date resolved, whether the event was serious or not (ICH criteria), relationship of the event to the study (1=none, 2=unlikely, 3=possible, 4=probable, 5=definitely), action taken, and whether the study was suspended or not.

All SAEs, regardless of causation, will be reported to REC within one week (in any SAE resulted in death, an immediate report within 24 hours will be sent.) Once a year the sponsor will summarize all SAEs and report these to REC. If at any point it is considered medically unsafe by the principal investigator for a patient to continue in the study, the patient will be excluded from the study and offered appropriate support.

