### 3.3 Intervention

The exercise training program includes three sessions per week over a 12-week period and will take place at CFAS or a local collaborator. The exercise intervention will start when baseline visits have been completed.

[figure not shown]

Figure 3 Exercise intervention, HRMax = Maximal Heart Rate.

The program consists of high intensity endurance training on ergometer bicycles. The intensity will progress throughout the 12 weeks of training. The training consists of 10 minutes of warm up at 40-60% maximum heart rate (HRmax), followed by 4 sets of 4 minutes of high intensity interval training (HR>85%HRmax) followed by 4 sets of 3 minutes of medium intensity (40-60% HRmax), for a total of 28minutes, and finally a 10 min cool-down of 50% HRmax fading to exercise cessation (see sFigure 3 Exercise intervention), for a total exercise time of 38-45 minutes. Previous studies in our centre have had significant results following this training program^17. Strenuous exercise is considered beneficial for SLE patients, and not considered harmful.

All sessions will be supervised and administered by CFAS personnel or local collaborators with experience in handling endurance exercise. To ensure proper intensity, all patients will be wearing a heart rate monitor. The maximal heart rate (HRmax) will be measured as the peak heart rate during the final minute of the VO2max test (see 3.9.2). To evaluate the precise amount of exercise completed for every patient, each training session will be documented (attendance, total time of HRmax > 85%, total time of exercise, average watt, average heart rate, and perceived exertion (BORG scale)).

The exercise session will be counted as successful if more than half of the high intensity training is above 85% of HRmax (so 8 minutes of the session), this is similar to previous studies. The time in each HR span of the patient for each training session will then be recorded to be measured for further compliance parameters.

Control groups will be encouraged to maintain current exercise habits for the duration of the study, and both groups will do a dietary and activity record at study baseline and followup.

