### 3.4 Criteria for discontinuation

Prior to each exercise session, the patient will be assessed regarding chest pain (acute or recurring). The termination criteria during exercise include onset of angina, confusion, nausea, severe pain in joints or muscles that prohibit further exercise, physical signs of profound fatigue, and verbal

communication of profound fatigue. If chest pain is present prior to exercise or any of the above-mentioned criteria occurs during exercise, the instructors are obliged to call one of the study-affiliated medical doctors immediately. If a patient experiences increased joint or muscle pain during the exercise, the medical doctor will be called to decide (in dialog with the patient) whether the exercise can continue or not.

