#### 4.11 Withdrawal from study

A patient may choose to end their participation in the study at any time. The patient will not be obliged to provide a reason, and the termination of participation will not influence future medical treatment nor have any other consequences for that patient, and this will be made clear to the patient when obtaining oral and written informed consent. The reason for discontinuation will be

documented (including “unknown reason”). In exceptional circumstances, the study investigator may choose to withdraw a patient from the study due to safety reasons determined by the study investigator.

The patient must have completed no less than 80% of the prescribed exercise (no less than 29 session or less than 32 minutes per session on average). This will be assessed at two weeks intervals, and subjects will be given two weeks to catch up on the missed sessions.

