6 STUDY POPULATION, ANALYSIS SET AND STATISTICAL PRINCIPLES

Eligibility criteria have been previously published³⁵. In brief, the participants suffered from systemic lupus erythematosus, and fulfilled 10 or more points on the 2017 ACR/EULAR SLICC⁴³, were not pregnant, did not suffer from diabetes mellitus and were 18 years or older, both males and females were included.

As stated earlier, sample size calculation required 40 completers, the study included 55 participants.

Randomization was done in a 1:1 ratio, stratified on sex.

The statistical analyses will be carried out primarily in the modified intention to treat (mITT) population, excluding the participants who were randomized but were found ineligible as per the ineligibility criteria within the first week of randomization, while retaining the data from all other study participants as randomized regardless of compliance and study completion. Supplementary per protocol (PP) analyses will exclude data from participants in the exercise group who failed to show up for 80% or more of the exercise sessions (29 or more sessions needed attendance to be considered in the PP group).

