12.3 Tables in supplement

eTable 1. Adherence to prescribed exercise.

eTable 2. Descriptive statistics of per protocol vs. protocol violators.

eTable 3. Self-reported diet, macronutrients and energy intake divided by intervention group.

eTable 4. Daily steps and METs in free-living conditions as reported by accelerometers.

eTable 5. Adverse reactions & events following randomization.

eTable 6. Other relevant characteristics measured at screening, baseline and followup, separated by intervention group at followup.

eTable 7. Baseline data grouped into the same percentiles of the IFN-score as table 3.

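### AE counts by arm are open to differential ascertainment: only the exercise arm has 36 supervised contacts, and no AE enquiry common to both arms is stated

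*Protocol*

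**What the plan says.** **How AEs are collected.** Protocol 4.8.1 sends to the CRF "All adverse events (AEs) and serious adverse events (SAEs) observed by the investigators", from consent to the last procedure, and its AE definition requires no causal link. Protocol 4.9 states "All AEs/SAEs related to the study assessments (including the exercise intervention) will be recorded immediately and notified in the CRF". It then says that every AE and SAE, expected or not, goes on a form and is published. Self-reports will also be collected, but without a stated time point, question or recall period. The form grades relationship to the study on five levels, starting at none. SAEs go to the ethics committee whatever their cause. The full procedure is in Appendix A, which is not in the supplied text.

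**Who is seen when.** Protocol 3.3 states "The exercise training program includes three sessions per week over a 12-week period" and "All sessions will be supervised and administered by CFAS personnel or local collaborators with experience in handling endurance exercise". Under Protocol 3.4 patients are assessed for chest pain before each session, and instructors must call a study doctor for a list of symptoms. Controls are asked to keep their current habits. Table 1 of the Protocol shows nothing for them between study day 4 and study day 93, and it has no row for an AE enquiry.

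**What is reported.** SAP 12.3 lists "eTable 5. Adverse reactions & events following randomization". SAP 13.3 and 14.3 list similar tables for the second and third papers. The SAP gives no method for AE analysis and does not mention unequal contact. SAP 11 describes the AE content of the first paper in terms of overuse complaints.

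**The concern.** An investigator can observe only what comes to notice. In the exercise arm, joint pain, an infection or a mild flare during the 12 weeks has up to three chances a week to be seen or mentioned. In a control the same event must be remembered and volunteered at follow-up, or reported unprompted. If the arms are then set side by side, a raw excess under HIIT mixes true harm with closer watching, and background lupus events noticed at sessions can look like harms of training. A randomised no-intervention control is what would allow these to be separated, provided events are captured alike in both arms. The distortion would run against the trial's own intervention.

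**Working it through.** **1. Number of sessions.** Three per week for 12 weeks (Protocol 3.3): 3 x 12 = 36. The plan's own figure confirms it. SAP 6 sets the per-protocol limit at 80% of sessions ("29 or more sessions needed attendance to be considered in the PP group"), and 0.80 x 36 = 28.8, which rounds up to 29.

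**2. Scheduled contacts after randomisation.** SAP 4 places randomisation after the baseline visits. Both arms then have visits 5 and 7, plus visit 6 for the PET subgroup (up to 40 patients, Protocol 3.9.12).

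| | Exercise | Control | Ratio |
|---|---|---|---|
| All sessions, no PET | 36 + 2 = 38 | 2 | 19 |
| All sessions, PET | 36 + 3 = 39 | 3 | 13 |
| 29 sessions, no PET | 29 + 2 = 31 | 2 | 15.5 |
| 29 sessions, PET | 29 + 3 = 32 | 3 | 10.7 |

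The adherence review in Protocol 4.11 ("This will be assessed at two weeks intervals") is not counted. It concerns completed sessions and minutes, which are logged at each session anyway, and it is not described as a meeting with the patient.

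**3. Is there an enquiry common to both arms?** Protocol 4.9 promises self-report without a schedule. Protocol 3.9.1 has a brief medical history at follow-up and 3.8.5 makes visit 5 identical to visit 2, but Table 1 marks medical history at visit 2 only. None of these sets out an AE question or a recall window.

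**4. What unequal capture would do.** Let the true proportion of patients with an AE be p in both arms. Then recorded proportion = p x capture, and recorded risk ratio = (p x capture in exercise) / (p x capture in control). The p cancels. The documents give no AE rate and no capture rate, so all inputs here are assumed: p = 50%, capture in exercise 90%, and 55 / 2 = 27.5 patients per arm. The recorded proportion in exercise is 0.50 x 0.90 = 45%. Missed control patients = 27.5 x 0.50 x (1 - capture).

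| Control capture | Recorded, control | Risk ratio | Control patients with an AE missed |
|---|---|---|---|
| 90% | 45% | 0.90/0.90 = 1.00 | 1.4 |
| 70% | 35% | 0.90/0.70 = 1.29 | 4.1 |
| 50% | 25% | 0.90/0.50 = 1.80 | 6.9 |
| 30% | 15% | 0.90/0.30 = 3.00 | 9.6 |

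In the exercise arm 27.5 x 0.50 x 0.10 = 1.4 patients are missed in every row. The ratios hold for any p; the missed counts scale with it.

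**The case against.** The strongest reply is that the quoted sentence is one route among several, and much of this reply stands.

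- A reader might infer that only events related to the study are recorded, and that 4.9 therefore contradicts 4.8.1. The text does not support this. The quoted sentence governs immediate recording; the next one covers all AEs and SAEs, and a scale that starts at no relationship presupposes that unrelated events are entered.
- A reader might infer that controls cannot have a study-related event. They can: they also do the maximal tests and the acute exercise bouts.
- Appendix A may already set equal collection. This cannot be excluded.
- Some channels serve both arms: medication changes (Protocol 3.5), blinded disease-activity scoring (Protocol 3.9.11), and the laboratory and questionnaire outcomes at 0 and 12 weeks. It would go too far to say that a control's flare or infection is likely to go unseen.
- The first paper's AE table is not the only safety output, its title does not mention arms, and no AE test is planned.
- The only routine question before a session is about chest pain, which is not a general AE enquiry.

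What this does not answer is the gap in contact and the absence, in the supplied text, of a scheduled enquiry common to both arms. The channels listed are not stated as AE sources, and any display by arm inherits the imbalance even without a test.

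**Conclusion.** The point holds as a risk of differential ascertainment, not as a demonstrated bias. The documents establish the imbalance in scheduled contact (38 against 2, or 39 against 3 with PET, at full attendance) and the lack of a stated common AE enquiry. They do not establish how many control events would be missed, so the risk ratios of 1.0 to 3.0 are an illustration on assumed capture; equal capture, and hence no distortion, lies within the range. The likely direction is against HIIT, mainly for non-serious events. SAEs are less exposed because they are reported whatever their cause. A reader might go further and say that AEs come mainly from training sessions, or that the comparison is biased. The documents rank no source, and Appendix A is unseen. The conclusion assumes that Appendix A does not already require the same enquiry in both arms.

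**What to change.** 1. Check Appendix A. If it already sets the same AE enquiry at the same times in both arms, state this in the SAP; step 4 then still applies.
2. If not, add one self-completed AE form to the visit 5 questionnaires, identical in both arms, covering all events whatever the cause over the same recall window. Self-completion suits follow-up staff who are blinded to allocation (Protocol 3.8).
3. For all participants, use sources collected alike in both arms: the documented medication changes and, if consent covers it, the same chart check over the same window. Consent needs confirming: Protocol 3.7 makes record access a condition of taking part, but 4.3 describes narrower purposes.
4. In the AE tables of SAP 12.3, 13.3 and 14.3, compare arms only on these symmetric sources. List events observed at training sessions separately for the exercise arm, without comparison.

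**Cost.** One page at an existing visit, a record check and a split table. Sample size and alpha do not change. With equal capture the spurious ratio is 1.00 whatever the true rate. Recall misses some minor events, to a similar degree in both arms. SAP 4 says recruitment stopped after 40 completers, so the form helps only participants who have not yet passed visit 5; the others rely on existing records.
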